DNA	Deoxyribonucleic acid
DSP	Diastolic blood pressure
EDC	Electronic data capture
ECG	Electrocardiogram
EMA	European Medicines Agency
EoS	End of Study
ET	Early Termination
FDA	Food and Drug Administration
HD	Huntington Disease
HDQoL	Huntington Disease Quality of Life Questionnaire
HR	Heartrate
ICC	Intra-class Correlation Coefficient
ICE	Intercurrent event
ICH	International Conference on Harmonisation

IOI	Inter-onset interval
IRT	Interactive Response Technology
IS	Independence scale
ITT	Intent-to-treat
LLOQ	Lower limit of quantification
LSM	Least square mean
MAR	Missing at random
MedDRA	Medical Dictionary for Regulatory Activities
MI	Multiple imputations
ML	Maximum-Likelihood
MMRM	Mixed Model Repeated Measures
MNAR	Missing not at random
mITT	Modified intent-to-treat
msec	Millisecond(s)
NfL	Neurofilament light chain
OLE	Open-label Extension
OR	Odds ratio
PBA-s	Problem Behaviors Assessment-Short form
PD	Protocol deviation
PIN _{HD}	Prognostic index normed for HD
PK	Pharmacokinetic(s)
PKP	PK Population
PMM	Pattern-mixture model
PP	Per Protocol
PROOF-HD	PRidopidine Outcome On Function in Huntington Disease
PT	Preferred term(s)
Q1	First Quartile
Q3	Third Quartile
QD	Once daily
Q-Motor	Quantitative Motor
QoL	Quality of life

QTcF	Fridericia-corrected QT interval
SAE	Serious adverse events
SAP	Statistical Analysis Plan
SBP	Systolic blood pressure
SD	Standard deviation
SE	Standard Error
SDMT	Symbol Digit Modalities Test
SMC	Safety Monitoring Committee
SoA	Schedule of Activities
SOC	System organ class
SP	Safety Population
SWR	Stroop Word Reading
TC	Telephone call
TEAE	Treatment-emergent adverse event(s)
TFC	Total functional capacity
TFL	Table, Figure, Listing
TMS	Total Motor Score
UHDRS	Unified Huntington's Disease Rating Scale
ULN	Upper limit of normal
V	Visit
VV	Virtual Visit(s)
W65PP	Per Protocol Week 65
W78PP	Per Protocol Week 78
Wk	Week
WOCBP	Women of childbearing potential

1. PREFACE

Huntington Disease (HD) is an autosomal dominant, progressive fatal neurodegenerative disorder characterized by motor, cognitive, and behavioral abnormalities. While medications to treat chorea and some behavioral symptoms are available, no therapy has yet proven able to modify the progressive and inexorable functional decline of the disease. A therapy that maintains functional capacity and prevents or delays the development of disability represents a critically unmet clinical need. The age of onset of the signs and symptoms of HD and the rate of disease progression can vary greatly. Adult-onset HD most often begins between 30 and 40 years of age. The illness generally lasts 15 to 20 years and is fatal. Following diagnosis, motor and cognitive functions steadily decline, ultimately leading to a state of immobility, dementia, and premature death.

The Statistical Analysis Plan (SAP) describes the planned analysis and reporting for Prilenia Therapeutics study PL101-HD301 (A Phase 3, Randomized, Double-Blind, Placebo-Controlled, Parallel Arm, Multicenter Study Evaluating the Efficacy and Safety of Pridopidine in Participants with Early Stage of Huntington Disease). The study is also referred to as the PRidopidine Outcome On Function in Huntington Disease Participants (PROOF-HD) study. The purpose of this Phase 3 study is to evaluate the efficacy and safety of pridopidine 45 mg twice daily (bid) as compared to placebo. Efficacy will be assessed for HD participants based on functional capacity using the Total Functional Capacity (TFC) score in the Unified Huntington's Disease Rating Scale (UHDRS) as the primary objective.

Some of the analyses in this SAP are included for the Safety Monitoring Committee (SMC). Details of what will be provided to the SMC will be included in the SMC Charter or analysis plan supporting it. Additional details of pharmacokinetics (PK) and pharmacogenomic analyses will be included in SAP addendum, appendix or separate SAPs.

The structure and content of this SAP provides sufficient detail to meet the requirements identified by the International Conference on Harmonisation of Technical Requirements for Registration of Pharmaceuticals for Human Use (ICH): E9 Guidance on Statistical Principles in Clinical Trials issued February 1998 as well as the ICH E9(R1) Addendum on Estimands and Sensitivity, November 2019.

The following documents were reviewed in preparation of this SAP:

- Clinical Study Protocol PL101-HD301, Version 7.0, Amendment 8.0, 10 November 2022
- Clinical Study Report (CSR) and subsequent analyses on the Phase 2 Study TV7820-CNS-20002, (PRIDE-HD – Pridopidine Dose Evaluation in Huntington's Disease) study
- Case report form (CRF) for PL101-HD301, V07, 3 May 2022
- ICH E9 Statistical Principles for Clinical Trials
- ICH E9(R1) Addendum on Estimands and Sensitivity Analysis in Clinical Trials
- ICH E3 Structure and Content of Clinical Study Reports

- Statistical Considerations for Clinical Trials During the Coronavirus Disease 2019 (COVID-19) Public Health Emergency
- Relevant publications indicated in references related to development of estimands, sensitivity analyses and handling of missing data

The reader of this SAP is encouraged to also read the clinical protocol for details on the conduct of this study, and the operational aspects of clinical assessments and timing for participant completion in this study. When differences exist in descriptions or explanations provided in the protocol and this SAP, the SAP prevails, and the differences will be explained in the CSR.

2. STUDY OBJECTIVES AND ENDPOINTS

The purpose of this Phase 3 study is to evaluate the effect of pridopidine 45 mg bid on functional capacity, as well as motor and behavioral features of HD in early-stage participants (HD Stages 1-2, Baseline TFC score of 7-13).

Objectives and Endpoints of the Main Study (Primary, Secondary and Safety):

Objectives	Endpoints
Primary	

 To assess the effect of pridopidine on functional capacity in participants with Stage 1-2 HD 	
 Change from Baseline to Week 65 in the UHDRS-TFC score
Multiplicity Adjusted Secondary Endpoints	
	Key Secondary (secondary endpoints are listed by order of hierarchy)

 To assess the effect of pridopidine on a composite measure of disease progression in participants with HD 	
 Change from Baseline to Week 65 in composite UHDRS (cUHDRS) total score
Secondary (secondary endpoints are listed by order of hierarchy)	

 To evaluate the effect of pridopidine on functional capacity, motor function, and other measures of efficacy over time in participants with HD 	
 Proportion of participants with improvement or no worsening (change from Baseline \geq 0 points) at Week 65 in UHDRS-TFC Change from Baseline to Week 52 in UHDRS-TFC score Change from Baseline to Week 78 in UHDRS-TFC score Change from Baseline to Week 65 in Quantitative motor (Q-Motor) [REDACTED] [REDACTED] Change from Baseline to Week 65 in UHDRS-Total Motor Score (TMS) Change from Baseline to Week 65 in Symbol Digit Modalities Test (SDMT) Change from Baseline to Week 52 in UHDRS-TMS score

	9. Proportion of participants with improvement or no worsening in Clinical Global Impression of Change (CGI-C) at Week 65
Non-multiplicity Adjusted Secondary Endpoints	

 • To evaluate the effects of pridopidine in participants with HD 	
 • Change from Baseline to Week 26 and 39 in the UHDRS-TFC • Proportion of participants with improvement or no worsening in UHDRS-TFC (change from Baseline ≥ 0) at Weeks 26, 39, 52 and 78 • Change from Baseline to Weeks 26, 39, 52 and 78 in cUHDRS • Proportion of participants with change from Baseline ≥ -1 in cUHDRS at Weeks 26, 39, 52, 65 and 78 • Change from Baseline to Week 26, 39 and 78 in the UHDRS-TMS score • Proportion of participants with improvement or no worsening in UHDRS-TMS (change from Baseline ≤ 0) at Weeks 26, 39, 52, 65 and 78 • Change from Baseline to Weeks 26, 39, 52, 65 and 78 in: 
 – UHDRS-TFC Scale sub-items (capacity to undertake domestic chores, activities of daily living, capacity to manage finances, care level and occupation) – UHDRS-TMS sub-scores for: 
 • Gait and balance score (defined as the sum of UHDRS-TMS domains gait, tandem walking, and retropulsion pull test) • Eye movement • Dystonia • Change from Baseline to Weeks 26, 39, 52 and 78 in SDMT

- Change from Baseline to Weeks 26, 39, 52, 65 and 78 in Stroop Word Reading (SWR)
- Change from Baseline to Weeks 26, 52 and 78 in Q-Motor [REDACTED]
[REDACTED]
[REDACTED]
- Proportion of participants with improvement or no worsening (change from Baseline \leq 0 milliseconds (msec) in Q-Motor [REDACTED]
[REDACTED]
[REDACTED]
- Change from Baseline to Weeks 26, 52, 65 and 78 in Q-motor [REDACTED]
[REDACTED]
[REDACTED]
- Responder analyses on CGI-C using different thresholds at Weeks 26, 39, 52, 65 and 78

Exploratory Endpoints

- To evaluate the exploratory efficacy effects of pridopidine in participants with HD
- To evaluate changes in disease biomarker, plasma neurofilament light chain (NfL), following treatment with pridopidine in participants with HD
- Change from Baseline to Weeks 26, 52, 65 and 78 in plasma NfL protein
- Relationship between Baseline NfL and changes from Baseline in select efficacy endpoints
- Relationship between changes from Baseline to Weeks 26, 52, 65 and 78 in NfL and select efficacy endpoints
- Proportion of participants with different thresholds for change from Baseline to Weeks 26, 52, 65 and 78 in plasma NfL levels


 To evaluate the PK of pridopidine and its main metabolite in participants with HD 	
 Plasma concentrations of pridopidine and its main metabolite at Weeks 26, 52, 65, and 78 and at last participants' visit Relationship between plasma concentration of pridopidine and clinical outcome measures
Safety and Tolerability Endpoints	

 To evaluate the safety and tolerability of pridopidine in participants with HD 	
 Incidence (count and rate) of adverse events (AEs) and serious AEs (SAEs) overall, by severity, by relationship to study drug, and those that led to withdrawal from the study treatment or study Incidence and shifts of clinically significant abnormalities in electrocardiogram (ECG), laboratory tests, vital signs, and abnormalities in physical and neurological exam Analysis of Columbia-Suicide Severity Rating Scale (C-SSRS) throughout the study Tolerability: 
 The number (%) of participants who complete the treatment period The number (%) of participants who fail to complete the treatment period due to AEs The number (%) of participants who fail to complete the treatment period meeting the QTcF-change, Creatinine Clearance (CrCl) or Psychiatric Stopping Rules

Objectives and Endpoints of the Open-Label Extension (OLE) Period:

Objectives	Endpoints
Efficacy	

 To evaluate the long-term treatment effect of pridopidine in participants with HD who previously completed the Main Study 	
 Proportion of participants with change from Baseline (Main Study) to each OLE visit in UHDRS-TFC ≥ -1

- Proportion of participants with change from Baseline (Main Study) to each OLE visit in UHDRS-TFC ≥ 0
- Change from Baseline (Main Study) to OLE visits in
 - UHDRS-TFC
 - cUHDRS
 - UHDRS-TMS
 - Quantitative motor (Q-Motor):
 - [REDACTED]
 - [REDACTED]
 - [REDACTED]
 - SDMT
 - SWR
- Change from Baseline (Main Study) to OLE visits in:
 - CGI-C
 - PBA-s
 - HDQoL

Safety and Tolerability Endpoints

- To evaluate long-term safety and tolerability of pri dopidone in participants with HD who previously completed the Main Study
- Incidence (count and rate) of AEs and SAEs overall, by severity, by relationship to study drug, and those that led to withdrawal from the study treatment or study
- Incidence and shifts of clinically significant abnormalities in ECG, laboratory tests, and vital signs
- Analysis of C-SSRS throughout the study
- Tolerability:
 - The number (%) of participants who completed the OLE treatment period
 - The number (%) of participants who failed to complete the OLE treatment period due to AEs

Biomarker Endpoints

• To evaluate long-term efficacy effects of pridopidine on NfL in participants with HD who previously completed the Main Study	
• Change from Baseline (Main Study) in NfL protein level to each OLE visit• Relationship between changes from baseline in NfL and selected efficacy endpoints in the OLE period
--	--

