8.3.1. Time Period and Frequency for Collecting AE and SAE Information

All AE and SAEs will be collected from the signing of the ICF until the last Follow-up visit at the timepoints specified in the SoA ([Table 2 – Main Study](#), and [Table 3 – OLE](#)). Assessment should be done through on-site clinic visits, safety TCs, and virtual visits (via telephone).

An event that emerged during or after treatment or worsened relative to the pretreatment state will be recorded as a treatment-emergent adverse event (TEAE).

All SAEs will be recorded and reported to the Sponsor or designee immediately upon any site study staff becoming aware and under no circumstance should this exceed 24 hours, as indicated in Appendix 3 (Section 10.3). The Investigator will submit any updated SAE data to the Sponsor within 24 hours of it being available.

Investigators are not obligated to actively seek AE or SAE after conclusion of the study participation. However, if the Investigator learns of any SAE, including death, at any time after a participant has been discharged from the hospital, and he/she considers the event to be reasonably related to the study drug or study participation, the Investigator must promptly notify the Sponsor.

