4.1.5. Safety Population (SP)

The safety population (SP) will include all randomized participants who received at least 1 dose of study drug. In this population, treatment will be assigned based upon the treatment participants actually received, regardless of the treatment to which they were randomized. The safety set will be used for safety analyses and biomarker analysis.

All participants who receive at least 1 dose of pridopidine during the OLE period will be included in the OLE safety population.

The actual treatment received in the double-blind period will be pridopidine if a participant receives pridopidine for >10% of total number of doses received; otherwise, the actual treatment will be placebo. The actual treatment received in the OLE will be pridopidine to pridopidine if a participant receives pridopidine for >10% of total number of doses received in the double-blind period; otherwise, the actual treatment will be placebo to pridopidine.

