8.2. Duration of Exposure

Duration of exposure to study drug (days treated) is the number of days on treatment based on the first and last days of treatment with the study drug (last day of study drug – first day of study drug + 1). In addition to summarizing overall treatment exposure in weeks, the weeks of exposure using the categories <13 weeks, ≥ 13 to <26 weeks, ≥ 26 to <39 weeks, ≥ 39 to <52 weeks, ≥ 52 to <65 weeks, ≥ 65 to <78 weeks and ≥ 78 weeks will be summarized using the number and percentage of participants exposed to study drug by treatment groups. In addition to the above intervals the number and percentage of participants exposed for ≥ 13 weeks, ≥ 26 weeks, ≥ 52 weeks, ≥ 65 weeks, ≥ 78 weeks will also be summarized.

Duration of treatment (days) will also be summarized by treatment group using descriptive statistics for continuous parameters as described in Section 5.4.

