8.4. Adverse Events

All AEs will be coded using MedDRA Version 23.0 (or a later version if updated during the study).

For statistical analysis, a TEAE is defined as an AE that occurs for the first time or worsens (as captured on the eCRF) on or after initiation of treatment in the corresponding analysis period (Main Study or OLE Treatment Period) EoS. Due to the short half-life of Pridopidine (10-12 hrs) AEs that started more than 14 days after end of treatment are not considered TEAEs.

The terms AEs and TEAEs are used interchangeably in this SAP and unless otherwise specified refer to TEAEs.

An overall summary will be presented by treatment groups that includes the number and percentage of participants who experienced at least one TEAE for the following categories: All TEAEs, serious TEAEs, TEAEs leading to study discontinuation, TEAEs leading to death, TEAEs based on maximal Severity, TEAEs leading to study drug withdrawal anytime during the study, TEAEs leading to study drug withdrawal during titration. When appropriate, a total column may appear as the last column.

Summaries will be presented for all TEAEs by SOC and PT for the following categories of TEAEs:

- TEAEs, severe TEAEs, Treatment-related TEAEs, Serious TEAEs (see below for more details), TEAEs potentially related to QT prolongation, (e.g., palpitations, dizziness, syncope, cardiac arrhythmias, and sudden death), TEAEs related to abuse potential (See Appendix 12.2 for the AE terms), TEAEs causing discontinuation from the study.

The above summaries will include the number of events as well as number and percentage of participants experiencing at least one TEAE in each SOC and PT. To count the number of participants with any TEAEs, a participant who experiences multiple TEAEs within the same SOC will be counted only once for that SOC (if the TEAEs are coded to the same PT). A participant who experiences multiple TEAEs coded to the same PT within the same SOC will be counted only once for that PT. The number and percentage of participants experiencing any TEAE will also be provided. All percentages will use the number of participants in the SP within that treatment group as the denominator. In the summaries SOCs will be sorted in descending order based on number of participants in Total column; PT within SOC will be sorted by descending number of participants in Total column.

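### TEAE incidence is reported without a person-time denominator, although time at risk varies widely within the Main Study and the open-label extension

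*SAP*

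**What the plan says.** The safety endpoint in SAP section 2 is "Incidence (count and rate) of adverse events (AEs) and serious AEs (SAEs) overall, by severity, by relationship to study drug". The OLE list in the same section uses the same count-and-rate form. No section says what rate means.

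SAP 8.4 sets out the tables. For the tables by system organ class (SOC) and preferred term (PT), "The above summaries will include the number of events as well as number and percentage of participants experiencing at least one TEAE in each" category. The overall table and the maximal-severity table specify only the number and percentage of participants. On the denominator: "All percentages will use the number of participants in the SP within that treatment group as the denominator". That population, under SAP 4.1.5, "will include all randomized participants who received at least 1 dose of study drug".

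The numerator has a cut-off: "AEs that started more than 14 days after end of treatment are not considered TEAEs". The SAP adds that "The terms AEs and TEAEs are used interchangeably in this SAP and unless otherwise specified refer to TEAEs", so the cut-off governs the AE tables generally. Protocol 8.3.1 has no such limit ("An event that emerged during or after treatment or worsened relative to the pretreatment state will be recorded as a treatment-emergent adverse event"), but the SAP states that it prevails where the two differ. Protocol 7.2 encourages participants who stop drug to remain in the study.

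SAP 8.2 summarises exposure by arm ("Duration of exposure to study drug (days treated) is the number of days on treatment", from first to last dose) but does not link it to the AE tables. Neither SAP section 8 nor protocol 9.4.5 contains a person-time rate.

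**The concern.** A participant who stops drug early leaves the TEAE numerator two weeks later but remains a full unit in the denominator. Two arms with the same underlying hazard can therefore show different percentages if they differ in how many participants stop and when. Unequal stopping is plausible: protocol 2.3.1 lists QT prolongation and reduced creatinine clearance as risks of the drug, and protocol 7.1 has stopping rules for both.

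In the OLE the difficulty needs no contrast between groups. Treatment continues to a common calendar end, so early entrants are at risk for about twice as long as late ones. A single percentage over that mixture has no stated duration, yet the OLE objective is long-term safety.

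**Working it through.** The AE plan states no figure to reproduce. Event hazards, stop times and stop rates by arm are not in the documents, so those below are assumptions, shown over a range.

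**Main Study, equal true hazards in both arms**

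Inputs:
- Participants who do not stop early: 72 weeks at risk, about 1.38 years (assumed, within the 65 to 78 weeks of the design).
- Early stops: 0.30 years on drug (assumed) plus the 14 days of SAP 8.4, which gives 0.30 + 14/365.25 = 0.338 years.
- Hazard λ = 0.3 or 0.6 per year (assumed).

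The probability of at least one event is p = 1 − exp(−λ × time). With a proportion d stopping early, the crude percentage is (1 − d) × p(1.38) + d × p(0.338). The gap between arms is therefore the difference in d multiplied by [p(1.38) − p(0.338)].

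| λ per year | p(1.38) | p(0.338) | Stops 30% v 15% | Gap | Stops 10% v 5% | Gap | Equal stops |
|---|---|---|---|---|---|---|---|
| 0.3 | 33.9% | 9.65% | 26.6% v 30.3% | 3.6 points | 31.5% v 32.7% | 1.2 points | 0 |
| 0.6 | 56.3% | 18.4% | 44.9% v 50.6% | 5.7 points | 52.5% v 54.4% | 1.9 points | 0 |

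Example, λ = 0.3: 0.70 × 33.9 + 0.30 × 9.65 = 26.6, and 0.85 × 33.9 + 0.15 × 9.65 = 30.3. First events divided by person-time at risk return λ in both arms in every row.

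Event counts do not remove the effect. A second set of assumptions uses 65 weeks for the others and stops at week 13, so 15 weeks at risk with the tail. Person-years per participant are then (0.70 × 65 + 0.30 × 15)/52 = 0.962 against (0.85 × 65 + 0.15 × 15)/52 = 1.106. With equal hazards the count ratio is 0.87. Under the same assumptions and a true hazard ratio of 1.2, the crude-percentage ratio is 0.98 to 1.04 for control-arm hazards of 0.05 to 1.0 per year.

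**When counted TEAEs cause the extra stops**

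Take the second set of assumptions with λ = 0.2. In each arm 15% stop for other reasons, and in one arm a further 15% stop because of a TEAE. Any-TEAE in that arm: 0.70 × 22.1 + 0.15 × 5.6 + 15 = 31.3%. In the other arm: 0.85 × 22.1 + 0.15 × 5.6 = 19.6%. The arm with more stops now looks worse on the any-TEAE row. For terms that did not cause the stops, shortened time at risk still lowers the percentage.

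**OLE**

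Protocol 4.4 plans recruitment from Q3 2020 to about Q4 2021, a span of roughly 12 to 18 months. The first entrants have 78 weeks of double-blind treatment and the last has 65, a difference of 13 weeks or about 3 months. The first entrants therefore start the OLE 9 to 15 months before the last participant completes. Adding the 12 months that follow gives 21 to 27 months, roughly 24, against 12 months for the last entrants.

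At λ = 0.3 per year, the cumulative incidence is 1 − exp(−0.3) = 26% at 12 months and 1 − exp(−0.6) = 45% at 24 months. For the Main Study it is 31% at 65 weeks (1.25 years) and 36% at 78 weeks (1.5 years).

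**The case against.** Several points on the other side are sound.

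- **The endpoint may already be met.** A reader might infer that the SAP promises a rate and fails to deliver it. The documents do not establish that. The SAP uses rate for percentages elsewhere: the 22.5% drop-out assumption in 3.3 and the completion figures of 98.9% and above 97% in 3.6.3.1 and 3.6.3.2. Count and rate can mean n and %, which 8.4 supplies. The term is undefined; a breach is not shown.
- **It is not only percentages.** The SOC/PT tables also carry event counts. This is correct, but the counts have no time base either.
- **A bias between arms is not demonstrated.** A reader might infer that the arm with more early stops will look safer. That requires unequal stopping, and the documents give no stop rate by arm. Planning assumed 22.5% in each group (SAP 3.3), and SAP 3.6.3.1 later calls discontinuation low. The direction can also reverse on the any-TEAE row, as shown in the working.
- **Early stopping is visible elsewhere.** SAP 8.2 tabulates exposure in bands, 8.4 reports TEAEs leading to drug withdrawal, and 3.2.8 makes stops due to AEs a tolerability endpoint. A reader can see differential exposure but cannot adjust event rates for it from those tables.
- **In the OLE, staggered entry alone favours neither group.** Both come from one randomisation and share a calendar end, and no table is split by entry date. This stands. What remains is that one pooled percentage has no defined duration.

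**Conclusion.** The plan has no exposure-adjusted AE incidence, and time at risk varies within both periods. For the Main Study the consequence is conditional: about 1 to 2 points for a 5-point gap in stopping, about 4 to 6 points for a 15-point gap, and nothing with equal stopping. This assumes constant equal hazards of 0.3 to 0.6 per year and stops at about 0.3 years, and it applies to events other than those that caused the stops. For the OLE the roughly twofold range in time at risk follows from the design and the planned recruitment dates. The crude percentage there cannot be read as a long-term incidence or set beside the Main Study figure. This is a worthwhile, low-cost improvement to the safety reporting. It is not an error that invalidates the planned tables.

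**What to change.** 1. In SAP 2 and 8.4, state what rate means.
2. Add to the overall TEAE table, and to the SOC/PT tables of TEAEs and of serious TEAEs, the number of participants with a first event per 100 participant-years at risk. Count time from first dose in the period to first event, or otherwise to the earlier of last dose + 14 days and end of period.
3. In the Main Study, give the between-arm rate difference with a 95% CI. In the OLE, give rates by group and in total.
4. Keep the crude percentages and event counts beside the rates.

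The dose dates are already used for exposure in SAP 8.2, and SAP 3.5.5 allows an addendum. The costs are a separate time-at-risk derivation for each SOC and PT and wider tables. The rate also assumes a roughly constant hazard, which is a reason to keep the crude figures.
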